## 8.2. Secondary Efficacy Endpoint

### 8.2.1. Patients Achieving Two or More Pre-specified Platelet Count

When considering the achieving two or more pre-specified platelet count, the visit with missing result will be excluded.

A logistic regression model will be performed on each endpoint defined in [Section 3.2.2.1](#) and include treatment, baseline platelet count and prior TPO-receptor agonist use, provided there are enough patients in each subgroup determined by each factor. The odds ratio for each active treatment effect compared to placebo (together with 95% CI and p-value) will be provided. Each endpoint will be summarized in number (%) of patients by treatment group.

For patients whose pre-specified platelet count achievement cannot be adequately determined, their achievement will be imputed using the same NRI approach as described in [Section 8.1](#).

Bar plots on proportions of patients achieving two or more pre-specified platelet counts on each defined endpoint and exact unconditional 95% CI will be provided by treatment group and combined active treatment group.

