4.2.2 Handling of Withdrawals

Subjects are free to withdraw from the study or study drug at any time upon request. Subject participation in the study may be stopped at any time at the discretion of the investigator or at the request of the sponsor.

Subjects who discontinue study drug or active participation in the study will no longer receive study drug. When a subject withdraws from the study drug or active participation in the study, the reason(s) for withdrawal shall be recorded by the investigator on the relevant page of the electronic case report form (eCRF). Whenever possible, all subjects who discontinue study drug permanently or withdraw from the study prematurely will undergo all end-of-study assessments. Subjects who fail to return for final assessments will be contacted by the site in an attempt to have them comply with the protocol. Following a minimum of 2 documented unsuccessful telephone calls, a registered letter will be sent to the subject in a final attempt to ensure protocol compliance.

It is vital to obtain follow-up data on any subject withdrawn because of an AE or SAE. In every case, efforts must be made to undertake protocol-specified safety follow-up procedures.

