### 3.2.2. Secondary Endpoints

#### 3.2.2.1. Patients Achieving Two or More Pre-specified Platelet Counts

- Patients able to achieve 2 or more consecutive platelet counts of  $\geq 30,000/\mu\text{L}$  separated by at least 5 days and without use of rescue medication
- Patients able to achieve 2 or more consecutive platelet counts of  $\geq 30,000/\mu\text{L}$  with an increase of platelet count of  $\geq 20,000/\mu\text{L}$  from baseline separated by at least 5 days and without use of rescue medication
- Patients able to achieve 2 or more consecutive platelet counts of  $\geq 50,000/\mu\text{L}$  separated by at least 5 days and without use of rescue medication
- Patients able to achieve 2 or more consecutive platelet counts of  $\geq 100,000/\mu\text{L}$  during the treatment period, separated by at least 5 days and without use of rescue medication
- Patients able to achieve platelet counts of  $\geq 50,000/\mu\text{L}$  at 3 of the last 4 visits.

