#### **4.3. Analysis Visit Window**

No analysis visit window is assigned. All data are summarized based on the visit name collected on the CRF page.

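### SAP 8.2.1 drops missing visits before the three-of-last-four platelet endpoint is applied, so a patient whose counts stop by Week 5 can meet it on early counts alone

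*SAP*

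**What the plan says.** SAP 3.2.2.1 (matching Protocol 7.2.1) lists five binary platelet endpoints. Four require two or more consecutive counts above a threshold, "separated by at least 5 days and without use of rescue medication". The fifth requires at least 50,000/µL "at 3 of the last 4 visits".

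SAP 8.2.1 covers all five: "A logistic regression model will be performed on each endpoint defined in" Section 3.2.2.1. It contains two rules for incomplete data:

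- "When considering the achieving two or more pre-specified platelet count, the visit with missing result will be excluded".
- "For patients whose pre-specified platelet count achievement cannot be adequately determined, their achievement will be imputed using the same NRI approach" as in Section 8.1.

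Neither section says when achievement counts as undeterminable, or which rule is applied first. SAP 4.3 adds "No analysis visit window is assigned", so visits are taken by their CRF name.

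On follow-up, Protocol 1.4 plans an end-of-treatment visit for a patient who stops treatment, and then observation for the intended study duration. Protocol 4.2.2 adds, where possible, that "all subjects who discontinue study drug permanently or withdraw from the study prematurely will undergo all end-of-study assessments".

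**The concern.** The three-of-last-four endpoint is the only one of the five that looks at the end of a patient's record. Its meaning depends on where that record ends. If missing visits are removed first, the last four become the last four with a result. For a patient whose data stop early, these lie in the first weeks of treatment. Such a patient can then succeed where a fully observed patient with the same early course fails, so losing data is scored better than losing response.

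The result is reported as an odds ratio against placebo with an unadjusted p-value. The primary endpoint (SAP 8.1.2) and the change from baseline (SAP 8.2.2) have sensitivity analyses for missing counts. The 8.2.1 endpoints have none that would expose the effect.

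**Working it through.** **The plan's own figure.** The documents give no power for this endpoint. The only stated power is 82.74% (SAP 4.4), for the primary endpoint: 24 vs 12 patients, 50% vs 1%, two-sided 5%. It reproduces with a pooled normal approximation and continuity correction:

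- Pooled rate = (24×0.50 + 12×0.01)/36 = 0.3367.
- Null SE = √(0.3367×0.6633×(1/24+1/12)) = 0.1671.
- Alternative SE = √(0.25/24 + 0.0099/12) = 0.1060.
- Correction = (1/24+1/12)/2 = 0.0625.
- z = (0.49 − 0.0625 − 1.960×0.1671)/0.1060 = 0.943, so power is 82.7%.

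Nothing below changes it.

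**Visit schedule.** From Protocol Table 2, platelet counts fall at Day 1, Day 4, Day 8 and Weeks 3, 5, 7, 9, 11 and 12. The nominal days are 1, 4, 8, 15, 29, 43, 57, 71 and 84. The last four scheduled on-treatment visits are therefore Weeks 7, 9, 11 and 12 (Days 43 to 84). A further count is scheduled at Week 16, and the endpoint's wording does not exclude it.

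**Applying the rule.** Take assumed counts of 12,000 at Day 1, 55,000 at Day 4, 80,000 at Day 8 and 70,000 at Week 3.

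| Data available | Four visits used | At least 50,000 | Result as written | Weeks 7, 9, 11, 12 with missing = not met |
|---|---|---|---|---|
| Ends at Week 5, any Week 5 count | D4, D8, W3, W5 | 3 or 4 | Met, about Day 29 | 0 of 4, not met |
| Ends at Week 3, Day 1 counted | D1, D4, D8, W3 | 3 | Met, Day 15 | 0 of 4, not met |
| Ends at Week 3, plus any withdrawal count | D4, D8, W3, withdrawal | 3 or 4 | Met | 0 of 4, not met |
| Completes, below 50,000 from Week 7 | W7, W9, W11, W12 | 0 | Not met | 0 of 4, not met |

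The first row is the firmest, because it uses four post-dose counts. The second relies on Day 1. Table 2 places Day 1 among the on-treatment visits, but Protocol 5.2 puts visit-day dosing after the tests, and SAP 4.2 lets a Day 1 count serve as baseline. Without Day 1 or a withdrawal count, a patient ending at Week 3 has only three counts and no set of four exists.

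**Size per patient.** One reclassified patient is 1/24 = 4.2 points in an active arm, or 1/12 = 8.3 points on placebo. As an illustration with assumed totals, against 0/12 on placebo, 7/24 gives Fisher p = 0.070 and 8/24 gives p = 0.033. The planned analysis is logistic regression, so this shows only that one patient can matter at this sample size.

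**Consecutive-count endpoints.** Adjacent visits from Week 3 are 13 to 14 days apart. Dropping one missed visit joins Week 3 to Week 7: 43 − 15 = 28 days, or 22 to 34 with ±3 days at each end. Dropping two joins Week 3 to Week 9: 57 − 15 = 42 days. For example, 60,000 at Week 3, Week 5 missing, 62,000 at Week 7 and everything else below 30,000 passes the 50,000 endpoint. It would fail if a missed visit broke the run.

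**The case against.** The best defence is that the two sentences can be read in the other order. Fix the last four scheduled visits, exclude those without a result, and an early leaver has nothing left to judge. Achievement then cannot be determined, and the non-responder rule applies. That reading is reasonable, but the text does not choose it. Read in the order written, the remaining counts do determine achievement, and the non-responder rule is never reached. Two programmers could report different rates.

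Other parts of the defence stand and limit the point:

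- **Not all five endpoints.** A reader might infer that an early leaver gains on every endpoint. Day 8 and Week 3 are adjacent and nominally 7 days apart, so high counts there meet a two-consecutive endpoint with nothing missing, whether or not the patient later loses response.
- **Stopping drug is not missing data.** The interruptions and discontinuations in Protocol Table 1 do not cancel platelet visits, and Protocol 1.4 keeps such patients under observation. Only lost counts trigger the rule.
- **No toxicity-driven bias is shown.** A reader might infer that dropout for adverse events would favour drug. The documents give no dropout or missingness by arm. The healthy-volunteer figures in Protocol 1.1 show no excess of subjects with events on drug: 19.4% vs 25.0% on placebo, and 27.8% vs 33.3%. Those studies are small and not in ITP, so they do not settle the matter, but they do not support the inference.
- **No maximum gap is specified.** For the consecutive endpoints, letting any missed visit break a run would penalise patients who miss a visit for unrelated reasons. That is a trade-off, not the correction of an error.

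**Conclusion.** The point holds for the three-of-last-four endpoint. As written, the SAP allows it to be met on counts ending at about Day 29, or at Day 15 if Day 1 or a withdrawal count is admitted as the fourth visit. A completer with the same start who loses response fails. The non-responder sentence does not clearly prevent this.

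The effect is 4.2 points per affected patient in an active arm. The number of such patients is unknown. Only patients with an early rise can benefit. If the drug works, they would sit mainly in the active arms even with equal missingness, but this is an inference and not something the documents quantify. The conclusion rests on applying the exclusion before selecting the last four visits, which the text permits but does not require. Taking Weeks 7, 9, 11 and 12 as the intended visits is also an inference, from the schedule.

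This is a secondary-endpoint definition to settle before database lock. For the four consecutive-count endpoints the long gaps are worth showing but are not a fault.

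**What to change.** In SAP 8.2.1:

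1. Define the last four visits as the scheduled on-treatment visits at Weeks 7, 9, 11 and 12.
2. Score a missing count at any of these as not meeting the threshold, and state that non-responder scoring takes precedence over exclusion for this endpoint.
3. Keep the present exclusion rule as a sensitivity analysis for this endpoint.
4. For the four consecutive-count endpoints, keep the present rule and add a sensitivity analysis in which a missing scheduled visit breaks the run.

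The cost is SAP wording and programming, with no new data. A patient who misses one of the four late visits can still qualify if the other three meet the threshold. One who misses two cannot, whatever the reason, so rates may fall slightly. The sensitivity analysis in item 3 would show by how much.

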7.7.4 Analysis of Secondary Endpoints

For each binary endpoint (ie, definition of subject achieving 2 or more consecutive platelet counts), a logistic regression model will be performed and include treatment, baseline platelet count and prior TPO-receptor agonist use, provided there are enough subjects in each

subgroup. The odds ratio for the treatment effect compared to placebo (together with 95% CI and p-value) will be provided.

Time to platelet response will be estimated using the Kaplan-Meier method. Each active treatment group curve will be compared against placebo curve using log-rank test. In addition, a proportional hazard model will be implemented as well with treatment, baseline platelet count, and prior TPO-receptor agonist use.

Change from baseline in the average of the last 2 platelet counts will be analyzed using an analysis of covariance with baseline platelets count as covariate, treatment, and prior TPO-receptor agonist use. Each active treatment group will be compared with placebo.

Summary statistics of the following subjects will be provided by each treatment group:

- Subjects receiving rescue medication during the treatment period
- Subjects with Grade 2 or higher non-skin bleeding event during the treatment or follow-up period

A subject will be considered to have an event if the event was observed at least once during the treatment period or follow-up period as mentioned above.

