#### **4.4. Sample Size**

A minimum of 60 patients will be enrolled in the study. Patients will receive either 200 mg BID or 400 mg BID of SKI-O-703 or placebo in a 2:2:1 ratio.

Based on [Podolanczuk et al \(2009\)](#) at least 50% of patients in the active treatment group will be responders (R). A sample size of 24 patients per active treatment group and 12 patients in the placebo group will provide approximately 82.74% power to detect a difference between response rates of 50% and 1% in the active treatment and placebo groups, respectively, at the 2-sided 5% significance level. The test statistic used in the sample size calculation was the 2-sided Fisher's Exact test using the normal approximation method.

Patients that do not receive the study drug or do not provide at least 1 post baseline measurement will be excluded from the analysis above and replaced.

There will be no adjustment for multiple comparisons. The sample size calculation was performed using PASS 15 Power Analysis and Sample Size Software (2017). NCSS, LLC. Kaysville, Utah, USA, [ncss.com/software/pss](http://ncss.com/software/pss).

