#### 8.1.1. Primary Analysis

The platelet responses after using rescue medication during treatment period will be set to missing and will be imputed as the average of the last 2 previous non-missing platelet counts. For example, if platelet count in Week 2 Day 8, Week 3 and Week 5 are 45,000, missing, and 48,000 respectively, the average will be calculated by results from Week 2 Day 8 and Week 5.

The primary efficacy endpoint will be summarized as overall platelet response rate (ORR) with exact unconditional 95% confidence intervals (CI) by treatment group. The ORR difference and exact unconditional 95% CI will be provided between each of active treatment groups and placebo group, and between two active treatment groups. The p-value from Fisher's exact test will be presented.

For patients whose ORR cannot be adequately determined, their ORR will be imputed using a non-responder imputation (NRI) approach.

Summary statistics will be provided on the number (%) of patients achieving platelet response by each treatment and the combined active treatment groups. The differences in the ORR, 95% CI and p-value from a Fisher's exact test will therefore be provided for:

- Each active treatment group (200 mg BID, 400 mg BID) vs. placebo
- Combine active treatment groups vs. placebo
- 200 mg BID vs. 400 mg BID.

A logistic regression model will also be performed on platelet response as dependent variable and treatment group, baseline platelet count and prior TPO-receptor agonist use as covariates. The odds ratio for the treatment effect compared to placebo (together with 95% CI and p-value) will be provided.

Bar plots on difference in proportions of ORR and exact unconditional 95% CI will be provided by treatment group and combined active treatment group.

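### The five binary platelet-count secondary endpoints rest on a logistic model with no named estimator or test, and it gives no usable odds ratio if none of the 12 placebo patients responds

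*SAP*

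**What the plan says.** SAP 8.2.1 fits a logistic regression to each endpoint listed in SAP 3.2.2.1, with treatment, baseline platelet count and prior TPO-receptor agonist use as terms. The output is stated as "The odds ratio for each active treatment effect compared to placebo (together with 95% CI and p-value) will be provided". Protocol 7.7.4 plans the same for every binary secondary endpoint: "a logistic regression model will be performed and include treatment, baseline platelet count and prior TPO-receptor agonist use".

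The model is conditional: "provided there are enough patients in each subgroup determined by each factor". No threshold is given, and nothing replaces the model if the condition fails.

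The other outputs in 8.2.1 are counts with percentages and bar plots of proportions, for which "exact unconditional 95% CI will be provided by treatment group and combined active treatment group". These describe each arm and do not compare arms.

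The primary endpoint is treated differently. SAP 8.1.1 plans a between-arm contrast, "The ORR difference and exact unconditional 95% CI will be provided between each of active treatment groups and placebo group", and a test, "The p-value from Fisher's exact test will be presented", with the logistic model in addition.

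SAP 4.4 gives arm sizes of 24, 24 and 12 and plans for "a difference between response rates of 50% and 1% in the active treatment and placebo groups". Those rates belong to the primary endpoint. Neither document gives a placebo rate for any secondary endpoint.

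**The concern.** A logistic model fitted by maximum likelihood has no finite treatment estimate when one arm has no events and the other has some. The placebo arm has 12 patients, and some of these endpoints are demanding, above all two consecutive counts of at least 100,000/µL. An empty placebo cell is therefore a realistic outcome.

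In that case the SAP leaves the reported result undetermined. A Wald p-value will be near 1 however large the effect. A likelihood-ratio, penalised or exact p-value may be well below 0.05. Nothing in the plan says which applies. The proviso does not help: it concerns numbers of patients, not of responders, so 12 placebo patients with no responder could satisfy it. If it is invoked, no between-arm inference remains.

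At stake is whether a clear effect on a secondary endpoint is reported as significant, non-significant or not estimable.

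**Working it through.** **Inputs.** Arms of 24, 24 and 12, planning rates of 50% and 1%, and stated power of 82.74% (SAP 4.4); two-sided 5% (SAP 4.1). All other response rates below are assumptions.

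**The plan's own figure.** Pooled rate (24×0.50 + 12×0.01)/36 = 0.3367. Pooled SE = √[0.3367×0.6633×(1/24+1/12)] = 0.1671. Unpooled SE = √(0.25/24 + 0.0099/12) = 0.1060. Continuity correction 0.5×(1/24+1/12) = 0.0625. Power = Φ[(0.49 − 0.0625 − 1.96×0.1671)/0.1060] = Φ(0.943) = 82.7%, as stated. Full enumeration of Fisher's test gives 93.9%. This figure is not in dispute.

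**Chance of an empty placebo cell**, (1 − p)^12:

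| Placebo rate | P(0 of 12) |
|---|---|
| 1% | 88.6% |
| 5% | 54.0% |
| 10% | 28.2% |
| 20% | 6.9% |

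**What the model then returns.** For 12/24 in each active arm and 0/12 on placebo, Newton iteration for maximum likelihood gives log odds ratio (SE) of 9.2 (28.8) after 8 steps, 16.2 (952) after 15 and 26.2 (141,350) after 25. The Wald p-values are 0.75, 0.99 and 1.00. The estimate is infinite, and the printed numbers depend on where iteration stops. An active arm with no responder has no estimable odds ratio at all.

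**P-values that do exist**, no covariates. For 12/24 against 0/12:
- Likelihood ratio: 2×[24 ln(1/2) − (12 ln(1/3) + 24 ln(2/3))] = 2×(−16.64 + 22.91) ≈ 12.56 on 1 df, p = 0.0004.
- Firth: without covariates this adds one half to each cell, so OR = (12.5/12.5)/(0.5/12.5) = 25.0, with penalised likelihood-ratio p = 0.0016.
- Fisher: p = 0.0025.

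| Active arm vs 0/12 | Wald | ML likelihood ratio | Firth LR | Fisher |
|---|---|---|---|---|
| 12/24 | near 1 | 0.0004 | 0.0016 | 0.0025 |
| 8/24 | near 1 | 0.006 | 0.021 | 0.033 |
| 7/24 | near 1 | 0.011 | 0.037 | 0.070 |
| 6/24 | near 1 | 0.020 | 0.065 | 0.079 |
| 5/24 | near 1 | 0.035 | 0.109 | 0.146 |

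With Wald among the candidates, the method decides significance in every row. Without Wald, it decides at 5, 6 and 7 of 24. Adding two simulated covariates left the pattern unchanged (7/24: likelihood ratio 0.013, Firth 0.048).

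**How often a significant result is obtained.** Exact enumeration of binomial(24) × binomial(12), two arms, no covariates; Wald counts only finite estimates:

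| Active vs placebo | Wald | Fisher | Firth LR |
|---|---|---|---|
| 50% vs 1% | 8% | 94% | 97% |
| 40% vs 1% | 4% | 75% | 86% |
| 30% vs 1% | 0.8% | 39% | 56% |
| 20% vs 1% | 0% | 8% | 17% |
| 50% vs 5% | 29% | 81% | 87% |
| 50% vs 10% | 38% | 65% | 71% |
| 50% vs 20% | 31% | 36% | 40% |

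**Type I error**, same enumeration, at common rates of 1, 5, 10, 20, 30, 40 and 50%:
- Firth LR: 0.02, 0.7, 1.8, 3.7, 4.5, 4.5 and 4.5%.
- Fisher: 0.02, 0.7, 1.6, 2.5, 2.7, 2.9 and 3.0%.
- Ordinary likelihood ratio: 5.8% at a common rate of 10% and 6.8% at 20%, so it is not a safe default.

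**The case against.** The best defence is that little depends on this. SAP 4.1 applies no multiplicity adjustment because the trial is Phase 2, the primary endpoint has its own exact analysis, and the responder counts will be tabulated, so any reader can compute Fisher's test. That stands and limits the severity.

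The placebo rate is also uncertain. Stable background corticosteroids and immunosuppressants are allowed (Protocol 5.8). Where a visit has several central results, or only local ones, SAP 8 takes the larger. The endpoint defined "at 3 of the last 4 visits" carries no rescue exclusion. All three could raise placebo response. Non-responder imputation pulls the other way. The 89% should therefore not be read as the probability for every endpoint.

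Where active rates are low the loss is small: at 20% vs 1% Fisher itself detects only 8%.

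A reader might infer that the sponsor will pick the method after seeing the data. The documents do not show this: the trial is double-blind and SAP 1 requires the SAP to be final before database lock. What they show is that the choice is not written down.

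A reader might also conclude that unadjusted Fisher should govern. That does not follow. It would displace the adjusted analysis that both documents plan, and it costs power (39% against 56% at 30% vs 1%), while Firth stays below 5% type I error at every rate checked.

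**Conclusion.** The gap is real. For five endpoints the only between-arm inference is a model that yields no usable odds ratio if placebo has no responder, and the p-value then depends on a method that the plan does not name. The loss is large when the active rate is high and the placebo rate very low (8% for Wald against 94% to 97% at 50% vs 1%), and small for rare endpoints. An empty placebo cell is most plausible for two counts of at least 100,000/µL, where an active arm may be empty as well.

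The secondary-endpoint rates are assumed, and the enumeration covers two arms without covariates. Type I error with the SAP covariates was not computed.

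It would be wrong to infer that the main efficacy conclusion is at risk. The Fisher test and exact intervals for the primary endpoint, and the log-rank test in SAP 8.2.3, do not depend on this model. Severity is minor to moderate.

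**What to change.** In SAP 8.2.1, and for the same model in 8.1.1, state in advance and regardless of the data that the covariate-adjusted odds ratio is estimated by Firth penalised logistic regression, with a profile penalised-likelihood 95% CI and a penalised likelihood-ratio p-value.

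In 8.2.1, also report for each endpoint and each active arm against placebo the risk difference, exact unconditional 95% CI and Fisher p-value already planned for the primary. Label them supportive, and state that they are reported always, including when the proviso withholds the model. Fixing these roles matters because the two can disagree, as at 7/24 vs 0/12. No change to SAP 8.1.2 or 8.2.3 is proposed, since nothing computed here supports one.

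The cost is SAP wording and modest programming, with no new data. Odds ratios shrink slightly, and their upper limits will be very wide when placebo is empty (for 12/24 vs 0/12 the Firth profile interval is 2.7 to 3,333). The risk difference is easier to read: its exact interval in that case is 16 to 70 percentage points.
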